10.0 SPECIAL STUDIES

10.1 Sample Collection Guidelines

Refer to Section 6.0 for tumor tissue and blood collection time points and Lab Manual for collection and processing details.

10.2 Specimen Banking

Patient blood and tissue samples collected for this study will be retained at the University of Michigan. Specimens will be stored indefinitely or until they are used up. If future use is denied or withdrawn by the patient, best efforts will be made to stop any additional studies and to destroy the specimens.

Specimen being stored long-term for potential use or not outlined in the protocol will be stored and used in compliance with the University of Michigan policy University Policy Governing Tissue Sample Collection, Ownership, Usage, and Disposition within all UMMS Research Repositories - <https://research.medicine.umich.edu/office-research/biorepository/governance-policies>.

11.0 STATISTICAL CONSIDERATIONS

The primary objective of the study is to determine the efficacy of ESK981 in combination with nivolumab therapy in patients with metastatic renal cell carcinoma who may have progressed despite treatment with one VEGF-TKI. Response rate, defined as the sum of complete + partial response (CR+PR), as measured

by RECIST v1.1 in Cohort B (combined therapy with ESK981 and Nivolumab) will be the primary statistical endpoint.

11.1 Study Design/Study Endpoints

A two-stage Mini-max Simon design will be used to minimize the number of patients to be treated with the combination therapy (Cohort B). We assume that this combination will not be of further interest if the true response rate were less than 0.25 and assume that a true response rate of at least 0.45 would be of clinical interest. This phase II study design permits early termination of patient entry due to futility of efficacy after the first 17 objective response evaluable patients have been accrued to Cohort B if there are 4 or less responses. If the study passes the first phase, then a second stage of 19 more objective response evaluable patients will be accrued for a total of 36 objective response evaluable patients. If 14 or more patients out of 36 have a response, then the treatment combination will be deemed successful. This trial design has 80% power to detect a response rate of 45% compared to a null rate of 25% assuming a 5% type I error. The probability of early termination with this design is 0.57 if the true response rate is 25%.

A single stage design will be used to determine efficacy of monotherapy treatment (Cohort A) with ESK981 efficacy in patients with metastatic renal cell carcinoma will be assessed as the RECIST v1.1 response rate. Assuming a response rate of clinical interest with monotherapy is 25% and null response proportion of 5% with a 1-sided type I error=0.102 there is 80% power with 11 patients to detect a response rate of 25%. Additionally, a futility analysis assuming a response rate of 25% would have 5% probability of 0 responses out of 11 patients. If 3 or more patients have a response with monotherapy ESK981, then the monotherapy treatment will be deemed of interest in a future study.

Secondary endpoints of the trial include assessment of toxicity in all patients who receive any study treatment. We will evaluate overall survival, progression free survival, duration of therapy, duration of response and QoL.

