11.2 Sample Size and Accrual

There are 2 cohorts for accrual with Cohort A being accrued first. Cohort B will follow and will have 2 stages of accrual. Cohort A will accrue 11 patients to monotherapy treatment. Then Cohort B will begin accrual of 17 patients to the first stage and if the interim analysis permits, the second stage will accrue an additional 19 patients. Our final sample size if all stages accrue will include 47 total objective response evaluable patients (11+17+19). We expect to accrue 1-2 patients per month for a total accrual period of 24 – 30 months.

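### Cohort A's success cut-off (3 or more responders of 11) does not have its stated error rates: power is 54%, not 80%, and type I error is 0.015, not 0.102

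*Combined protocol and SAP*

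**What the plan says.** Section 11.1 introduces the cohort with "A single stage design will be used to determine efficacy of monotherapy treatment (Cohort A"), using RECIST v1.1 response. The planning assumptions follow: "Assuming a response rate of clinical interest with monotherapy is 25"%, and a "null response proportion of 5% with a 1-sided type I error=0.102 there is 80% power with 11 patients to detect a response rate of 25"%. It adds that "a futility analysis assuming a response rate of 25% would have 5% probability of 0 responses out of 11 patients". The paragraph closes with the only success criterion given for this cohort: "If 3 or more patients have a response with monotherapy ESK981, then the monotherapy treatment will be deemed of interest in a future study".

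The Statistical Methodology row of the synopsis repeats the type I error, power and sample size but gives no cut-off. Section 11.2 confirms the size ("Cohort A will accrue 11 patients to monotherapy treatment") and counts these 11 among the 47 response-evaluable patients. No other part of the document gives a different cut-off for Cohort A.

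**The concern.** With a fixed sample of 11 and a binary endpoint, the number of responders required for success fully determines the type I error and the power. A reader will take the one cut-off in the paragraph to be the rule that carries the error rates stated just before it. It does not. The stated figures belong to a cut-off one responder lower.

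At stake is the conclusion on secondary objective 2.2.1 (endpoint 2.5.1). If 2 of 11 patients respond, the monotherapy fails the written rule but passes the rule whose error rates are stated. The protocol would then support either conclusion, and the choice would be made with the result already known.

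**Working it through.** **Inputs**, all from Section 11.1, with n repeated in Section 11.2:

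- n = 11
- null rate p0 = 0.05
- rate of interest p1 = 0.25
- stated one-sided type I error 0.102
- stated power 80%
- written success rule: at least 3 responders

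**Formula.** With X binomial(11, p) and success declared when X ≥ r, the type I error is P(X ≥ r | 0.05) and the power is P(X ≥ r | 0.25).

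**Step 1. Reproduce the stated figures.** They appear at r = 2:

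- Type I error: 1 − 0.95^11 − 11 × 0.05 × 0.95^10 = 1 − 0.5688 − 0.3293 = 0.1019, which rounds to the stated 0.102.
- Power: 1 − 0.75^11 − 11 × 0.25 × 0.75^10 = 1 − 0.0422 − 0.1549 = 0.8029, the stated 80%.

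**Step 2. Apply the written rule, r = 3.** Remove the probability of exactly 2 responders from each tail:

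- P(X = 2 | 0.05) = 55 × 0.05² × 0.95^9 = 0.0867, so type I error = 0.1019 − 0.0867 = 0.0152.
- P(X = 2 | 0.25) = 55 × 0.25² × 0.75^9 = 0.2581, so power = 0.8029 − 0.2581 = 0.5448.

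**Step 3. Check that no other cut-off fits.**

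| Success if responders ≥ | Type I error (p = 0.05) | Power (p = 0.25) |
|---|---|---|
| 1 | 0.431 | 0.958 |
| 2 | 0.1019 | 0.8029 |
| 3 (as written) | 0.0152 | 0.5448 |
| 4 | 0.0016 | 0.287 |

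Only 2 or more matches the stated pair.

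**Step 4. Check the sample size.** For the rule of 2 or more, power at 25% is 0.756 with 10 patients and 0.803 with 11, so 11 is the smallest size reaching 80%. For the rule of 3 or more, 80% power is first reached at 16 patients (type I error 0.043, power 0.803). The sample size therefore also points to a cut-off of 2.

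**Step 5. Check whether an approximation explains the figures.** The one-sided normal approximation to the power is Φ{[(p1 − p0)√n − z√(p0(1 − p0))] / √(p1(1 − p1))}. With z set for a type I error of 0.102 it gives 81.4%. The two-sided version gives 76.1%. Neither connects 0.102 and 80% with a cut-off of 3.

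**Step 6. The futility sentence.** P(0 of 11 | 0.25) = 0.75^11 = 0.042, close to the stated 5%. This describes a result of no responses and says nothing about the success cut-off.

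**The case against.** The arithmetic is not in dispute. The best counter-argument is that the final sentence never says it is the rejection region of the 0.102 test, so 3 may be a deliberate, stricter criterion. There are two natural reasons for choosing it. First, 3/11 = 27.3% is the smallest observed rate that reaches 25% (2/11 = 18.2% does not). Second, 3 of 11 is the smallest count whose exact 95% interval, the interval planned in Section 11.4, excludes 5%: the lower limit is 6.0% for 3 of 11 and 2.3% for 2 of 11. A cut-off of 3 also lowers the false-positive risk from 10.2% to 1.5%, so the discrepancy is not purely a loss.

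It can also be said that little depends on it. Cohort A is secondary. Under Section 11.3, Cohort B opens on Cohort A's toxicity, not its response count. Section 11.4 plans a count, a proportion and an interval for each cohort, and these are the same under either rule.

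Part of this stands. The document does not prove which number is the slip, although the three-decimal 0.102 and the choice of 11 patients both favour 2. The practical effect is limited to whether the monotherapy is labelled worth further study. The contradiction remains, however: neither reason for 3 is written down, and if either was intended, the stated type I error and power are wrong for the only success rule given.

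**Conclusion.** The concern holds. The written rule has type I error 0.015 and power 54%, against the stated 0.102 and 80%. At a true response rate of 25%, the chance of not declaring the monotherapy of interest is 1 − 0.545 = 46%, against the 20% the plan implies. These are exact results for 11 response-evaluable patients with independent outcomes and a cut-off applied as written.

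This should be corrected, because a pre-specified decision rule contradicts its own stated properties. The scope is limited to Cohort A. The Cohort B rule (stop at 4 or fewer of 17, success at 14 or more of 36) reproduces its stated properties: type I error 0.044, power 0.800, and early-termination probability 0.574 at a 25% response rate.

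**What to change.** Choose one of two corrections before the Cohort A response result is known:

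1. Change the success sentence in Section 11.1 to 2 or more responders of 11. This agrees with every other Cohort A design figure, and the synopsis needs no change.
2. Keep 3 or more, give the reason for it, and restate the one-sided type I error as 0.015 and the power as 54% in both Section 11.1 and the Statistical Methodology row of the synopsis.

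In either case, adding the cut-off to the synopsis would keep the two places aligned. Both corrections are changes of wording only and need no more patients. Keeping 3 or more together with 80% power would instead need 16 patients in Cohort A, five more than planned, and the type I error would then be 0.043.

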11.2 Sample Size and Accrual

There are 2 cohorts for accrual with Cohort A being accrued first. Cohort B will follow and will have 2 stages of accrual. Cohort A will accrue 11 patients to monotherapy treatment. Then Cohort B will begin accrual of 17 patients to the first stage and if the interim analysis permits, the second stage will accrue an additional 19 patients. Our final sample size if all stages accrue will include 47 total objective response evaluable patients (11+17+19). We expect to accrue 1-2 patients per month for a total accrual period of 24 – 30 months.

11.3 Early Stopping Due to Toxicity

Toxicity will be assessed in each cohort. If the DLT proportion is >30% during cycle 1 in Cohort A then dosing as is planned for the combination cohort will require modification before Cohort B can begin. Accrual of Cohort B will not begin until toxicity assessment of Cohort A is complete.

Cohort B will assess DLT proportions in the first 6 patients. If 2 or more DLTs occur in the first 6 patients of Cohort B, then dosing in the combination treatment in Cohort B will be decreased one dose level. If a decreased dose level is opened, assessment of another 6 patients will be assess for DLTs; if 2 or more DLTs occur then the trial will be halted. Accrual will be held during toxicity evaluation.

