Nivolumab (Opdivo) a PD-1 antibody, is FDA approved for the treatment of advanced renal cell carcinoma after disease progression on prior anti-angiogenic therapy. In the CHECKMATE-025 trial, nivolumab demonstrated improved overall survival compared with everolimus in the randomized clinical trial setting (25 months vs 19.6 months, HR 0.73, p-value 0.0018) [34].

ESK 981 in combination with anti-PD1 immunotherapy

VEGF inhibition in combination with immunotherapy in the form and anti-PD1 or anti-PD-L1 therapy has already been demonstrated in other drug combinations. Bevacizumab, an anti-VEGF therapy, in combination with atezolizumab (anti-PD-L1), was studied in ten patients with previously untreated metastatic RCC, and was well-tolerated. In this small cohort, there were 4 partial responses and 4 patients with stable disease [35]. A randomized multi-arm phase III clinical trial is currently ongoing evaluating the combination of lenvatinib, a multikinase inhibitor, with either everolimus or pembrolizumab compared with sunitinib in patients with advanced renal cell carcinoma (NCT02811861).

Given the superior activity of ESK981 compared to other small molecule VEGFR inhibitors especially potent inhibition of Tie-2 and additional autophagy inducing activity of ESK981, and the emerging clinical data on synergy between VEGFR inhibition and anti-PD1/L1 antibody immunotherapy, we propose a two-cohort phase II study. We first seek to evaluate the safety of ESK981 monotherapy in a safety cohort of 11 patients (Cohort A), after which accrual of Cohort B will begin, with a safety lead-in of six patients to establish a safe dose of ESK981 in combination with flat dose nivolumab at 480 mg IV. Subsequently, an expansion of Cohort B will be accrued to evaluate the clinical efficacy of the combination of ESK981 at the previously established safe dose in conjunction with nivolumab. Subjects in cohort A cannot cross-over into Cohort B.

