8.9 Early Stopping Rules

See section 11.3 for Early Stopping Due to Toxicity.

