9.2 Nivolumab

- Other names for the drug: Opdivo
- Description: Injection: 40 mg/4 mL and 100 mg/10 mL solution in a single-dose vial.
- Classification - type of agent: immunomodulatory; checkpoint inhibitor
- Mode of action:
Binding of the PD-1 ligands, PD-L1 and PD-L2, to the PD-1 receptor found on T cells, inhibits T-cell proliferation and cytokine production. Upregulation of PD-1 ligands occurs in some tumors and signaling through this pathway can contribute to inhibition of active T-cell immune surveillance of tumors. Nivolumab is a human immunoglobulin G4 (IgG4) monoclonal antibody that binds to the PD-1 receptor and blocks its interaction with PD-L1 and PD-L2, releasing PD-1 pathway-mediated inhibition of the immune response, including the anti-tumor immune response. In syngeneic mouse tumor models, blocking PD-1 activity resulted in decreased tumor growth.
- Pharmacokinetics:
Nivolumab pharmacokinetics (PK) was assessed using a population PK approach for both single-agent OPDIVO and OPDIVO with ipilimumab.

OPDIVO as a single agent: The PK of single-agent nivolumab was studied in patients over a dose range of 0.1 to 20 mg/kg administered as a single dose or as multiple doses of OPDIVO every 2 or 3 weeks. Nivolumab clearance decreases over time, with a mean maximal reduction (% coefficient of variation [CV%]) from baseline values of approximately 24.5% (47.6%) resulting in a geometric mean steady state clearance (CLss) (CV%) of 8.2 mL/h (53.9%); the decrease in CLss is not considered clinically relevant. The geometric mean volume of distribution at steady state (Vss) (CV%) is 6.8 L (27.3%), and geometric mean elimination half-life (t_{1/2}) is 25 days (77.5%). Steady-state concentrations of nivolumab were reached by approximately 12 weeks when administered at 3 mg/kg every 2 weeks, and systemic accumulation was approximately 3.7-fold. The exposure to nivolumab increased dose proportionally over the dose range of 0.1 to 10 mg/kg administered every 2 weeks.
- Side effects:
OPDIVO as a single agent: fatigue, rash, musculoskeletal pain, pruritus, diarrhea, nausea, asthenia, cough, dyspnea, constipation, decreased appetite, back pain, arthralgia, upper respiratory tract infection, and pyrexia.
- Drug Interactions:
No formal pharmacokinetic drug-drug interaction studies have been conducted with OPDIVO.
- Storage and stability:
The product does not contain a preservative. After preparation, store the OPDIVO infusion either:

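### Section 11.3 sets no toxicity rule that pauses accrual in Cohort A, and none for Cohort B after its lead-in, while the synopsis safety condition on stage 2 is undefined

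*Combined protocol and SAP*

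**What the plan says.** Section 8.9 is a single pointer: "See section 11.3 for Early Stopping Due to Toxicity". Section 11.3 is therefore the only stopping section for toxicity.

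- **Cohort A.** Section 1.3 describes the aim as to "evaluate the safety of ESK981 monotherapy in a safety cohort of 11 patients", and Section 11.2 says "Cohort A will accrue 11 patients to monotherapy treatment". The rule in 11.3 is "If the DLT proportion is >30% during cycle 1 in Cohort A then dosing as is planned for the combination cohort will require modification", and that change must come before Cohort B opens. It adds: "Accrual of Cohort B will not begin until toxicity assessment of Cohort A is complete".
- **Cohort B.** "Cohort B will assess DLT proportions in the first 6 patients". The condition "If 2 or more DLTs occur in the first 6 patients of Cohort B" leads to a decrease of one dose level and a further 6 patients. Two or more DLTs in those 6 halt the trial. A closing sentence holds accrual while toxicity is evaluated, without naming a cohort.
- **The 17-patient look.** Section 11.1 stops Cohort B for 4 or fewer responses in 17 response-evaluable patients. It has no toxicity criterion.
- **Synopsis (study product row).** The 19 additional Cohort B patients are to be accrued only if no safety signals have been found. No signal is defined.
- **General oversight.** Section 13.0 provides for DSMC oversight with quarterly reports, and Section 5.6 lists termination by the institution. Neither states a toxicity threshold.

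**The concern.** The plan calls Cohort A a safety cohort and gives it a DLT threshold, but meeting that threshold affects only the next cohort. Once a fourth DLT has occurred among the 11, the threshold is exceeded whatever follows, and 11.3 does not say what happens to the Cohort A places not yet filled.

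In Cohort B, a lead-in with 0 or 1 DLT in 6 ends the numerical rule, although 30 of the 36 planned patients are still to come. Six patients give limited protection against passing by chance. The synopsis appears to intend a safety check before stage 2, but the operative sections do not contain it. At the moment stage 2 opens, the team would have a response count to apply and no agreed toxicity count.

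**Working it through.** **Inputs.** Cohort A: 11 patients, threshold above 30% (11.2, 11.3). Cohort B: 2 or more DLTs in 6 (11.3); 17 + 19 = 36 patients (11.1). DLT window: cycle 1, 28 days (5.1). Accrual: 1 to 2 patients per month (11.2). The documents give no expected DLT rate, so true rates p of 20% to 50% are assumed, and patients are treated as independent.

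**Plan's own figures.** No operating characteristic is stated for the toxicity rules, so there is none to reproduce. The stated early-termination probability of 0.57 is used below and does reproduce: P(4 or fewer responses of 17 at 25%) = 0.574.

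**Coverage.** After a passed lead-in, 36 − 6 = 30 of 36 Cohort B patients (83%) have no numerical toxicity rule. After a dose decrease it is 24 of 36 (67%) if the first 6 count toward the 36, or 30 of 42 treated (71%) if they do not.

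**Cohort A.** 3/11 = 27.3% and 4/11 = 36.4%, so above 30% means 4 or more. The fourth DLT falls at patient j with probability C(j−1, 3) p⁴ (1−p)^(j−4), for j = 4 to 11.

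| True DLT rate | P(4 or more of 11) | Mean position of 4th DLT, if reached | Slots left | Avoidable, 1 already enrolled | Avoidable, 2 already enrolled |
|---|---|---|---|---|---|
| 40% | 0.704 | 7.98 | 3.0 | 2.1 | 1.4 |
| 50% | 0.887 | 7.27 | 3.7 | 2.8 | 2.0 |

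Slots left are 11 minus the mean position. The last two columns average max(0, 11 − j − d) for d = 1 or 2, because a 28-day window and 1 to 2 enrolments per month mean one or two patients may already be in when the fourth DLT is known.

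**Cohort B lead-in.** P(pass) = (1−p)⁶ + 6p(1−p)⁵.

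- 40%: 0.0467 + 0.1866 = 0.233
- 50%: 0.0156 + 0.0938 = 0.109

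If all 30 later patients are treated, expected DLTs are 30 × 0.4 = 12 and 30 × 0.5 = 15. If the response rate is the null 25%, stage 2 opens with probability 1 − 0.574 = 0.426. Later patients then average 11 + 0.426 × 19 = 19.1, giving about 7.6 and 9.5 DLTs.

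**Illustration: the plan's 30% threshold at 17 patients.** 5/17 = 29.4% and 6/17 = 35.3%, so the flag is 6 or more. After 0 DLTs in the lead-in, 6 or more of the next 11 are needed; after 1, 5 or more of 11.

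- 40%: (0.0467 × 0.2465 + 0.1866 × 0.4672) / 0.2333 = 0.42
- 50%: (0.0156 × 0.5000 + 0.0938 × 0.7256) / 0.1094 = 0.69

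The same formula gives 0.035 at 20% and 0.17 at 30%. For comparison, P(4 or more of 11) in Cohort A is 0.16 at 20% and 0.43 at 30%.

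**The case against.** A fair defence has four parts.

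1. **Safeguards outside 11.3.** The synopsis ties stage 2 to safety, the DSMC reviews the trial quarterly under an institutional plan not included here, and the institution can terminate. DLTs are to be entered within one business day (12.0), SAEs go to the Coordinating Center within 24 hours (8.6), and 5.2 sets hold and discontinuation rules for each patient. This stands. A reader might infer that no toxicity result could ever stop accrual; the documents do not support that. What is missing is a stated criterion. The rules in 5.2 act on patients already treated, not on whether new ones are enrolled.

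2. **11.3 is silent about Cohort A; it does not order enrolment to continue.** Correct. Its closing accrual hold could be read to cover Cohort A. But that sentence ends the Cohort B paragraph, and no evaluation during Cohort A accrual is defined that would trigger it.

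3. **The later exposure may be smaller.** Also correct. Enrolment overlaps the DLT window, and stage 2 may not open. Both are allowed for in the figures above.

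4. **A count in the 17 would miss early toxicity.** Those 17 are response-evaluable. A patient who leaves for toxicity before completing two cycles, without objective progression, is not evaluable under 7.1.1 and is replaced under 5.7. This is a valid limit on any such check, so the denominator must be toxicity-evaluable patients.

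A reader might also argue that a one-cycle lead-in is too short because Section 9.2 says "Steady-state concentrations of nivolumab were reached by approximately 12 weeks". That sentence refers to 3 mg/kg every 2 weeks, whereas this trial uses a 28-day nivolumab schedule for which 9.2 gives no time to steady state. The point here does not rely on it.

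**Conclusion.** The gap is real and limited. Section 11.3 has no pre-specified rule that pauses Cohort A accrual, and no numerical toxicity rule for Cohort B once the lead-in, or the repeat lead-in at a lower level, is passed. The synopsis condition on stage 2 has no definition and does not appear in 5.1 or 11.1 to 11.3, so those sections must be reconciled.

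The practical size in Cohort A is about 1.4 to 2.8 avoidable enrolments after the plan's own threshold is certain, across true rates of 40% to 50%. In Cohort B, between about 1 in 4 and 1 in 9 combinations with such rates would pass the lead-in and meet no further numerical rule. These figures rest on assumed, constant, independent DLT rates. General oversight softens the gap without closing it, because these documents give it no threshold to apply. It should be corrected; it does not undermine the efficacy design.

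**What to change.** 1. In 11.3, state that Cohort A accrual pauses for DSMC review once the fourth cycle 1 DLT is recorded.
2. Reconcile the synopsis with 5.1, 11.1 and 11.3 by adding a toxicity review to the existing 17-patient look, before stage 2 opens. Count all toxicity-evaluable patients as defined in 7.1.1, including those replaced as not response-evaluable, separately by dose level. The plan's own 30% threshold is one available criterion. State it as a proportion, since the denominator may exceed 17: 6 DLTs exceed 30% of 19 (31.6%) but not of 20 (30.0%).

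The sponsor-investigator and DSMC set the final criterion and decide any dosing action after a pause.

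**Cost.** A few sentences, with no added patients or visits. At a true DLT rate of 20%, the chance of a Cohort A pause is 16%, and the chance of a flag at patient 17 after a passed lead-in is about 3.5%. At 30% these are 43% and 17%. A Cohort A pause at the eleventh patient would cost no enrolment. The 17-patient review still leaves stage 2 without a later numerical count; whether to add one is for the sponsor and DSMC to judge.
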